6.2.2.6 Handling of Incomplete Dates for AL002 Dosed Participants

If the start date of the AE is incomplete and the AE end date is not prior to the first dose date of AL002, then the month and year (or year alone if month is not recorded) of onset determine whether an AE is treatment emergent. The event is considered treatment emergent if both of the following 2 criteria are met:

- The AE start date is the same as or after the month and year (or year) of the first dose date of AL002, and
- The AE start date is the same as or before the month and year (or year) of the date corresponding to 90 days after the last dose date of AL002.

An AE with completely missing start and end dates, or with the start date missing and an end date later than the first dose date of AL002, will be considered treatment emergent. In addition, an AE with the start date missing and incomplete end date with the same or later month and year (or year alone if month is not recorded) as the first dose date of AL002 will be considered treatment emergent.

An imputation will be done for partial dates in order to compute an estimated study day for display in the listing. For partial start dates:

- If the year is unknown, then the date will be assigned the first dose date of AL002.
- If the month is unknown, then:
 - a) If the year matches the year of the first dose date of AL002, then the month and day of the first dose date will be imputed.
 - b) Otherwise, ‘January’ will be assigned.
- If the day is unknown, then:
 - a) If the month and year match the month and year of the first dose date of AL002, then the day of the first dose date will be imputed.
 - b) Otherwise, ‘01’ will be assigned.

For partial end dates:

- If the year is unknown, then the date will be assigned the last participation date of AL002.
- If the month is unknown, then:
 - a) If the year matches the year of the last participation date of AL002, then the month and day of the last participation date will be imputed.
 - b) Otherwise, “December” will be assigned.
- If the day is unknown, then:
 - a) If the month and year match the month and year of the last participation date of AL002, then the day of the last participation date will be imputed.
 - b) Otherwise, the last day of the month will be assigned.

If the imputation takes the start date past the known end date, then the start date will be set to the day before the end date. If the imputation takes the end date prior to the known start date, then the end date will be set to the day after the start date.

The first dose date of AL002 is defined in Section 3.2.

6.2.2.7 Deaths

Deaths will be captured as SAEs according to the methods described above.

6.2.3 Columbia-Suicide Severity Rating Scale (C-SSRS)

Two versions of the C-SSRS were used in the Core Study: a Screening/Baseline version and a Since Last Visit version. The Screening/Baseline version of the C-SSRS assesses the lifetime suicidal ideation and behavior and non-suicidal self-injurious behavior, the suicidal ideation in the past 6 months and suicidal behavior and non-suicidal self-injurious behavior in the past 2 years. The Screening/Baseline version of the C-SSRS was administered on Core Study Day 1 prior to dosing. The Since Last Visit version of the C-SSRS assesses suicidal thoughts or behaviors the participant may have had since the last time the C-SSRS was administered as specified in the Schedules of Assessments in the protocol.

6.2.4 Laboratory Data

Collection schedules for hematology, blood chemistry, urinalysis testing, and coagulation are specified in the Schedules of Assessments in the protocols.

Indicators of values below or above a limit of quantitation (the lower limit of quantitation (LLOQ) or the upper limit of quantitation (ULOQ)) will be included, as well as all LLOQ or ULOQ limits. When values are below or above a limit of quantitation, they will be listed as such, and the closest imputed value will be used for calculating summary statistics as specified in Section 7.1.4.

Laboratory results will be assigned toxicity grades by the central laboratory based on the Common Toxicity Criteria for AEs (CTCAE) V5.0, when applicable. For a laboratory test, if the alert flag was normal and the toxicity grade was absent, then the toxicity grade will be assigned zero, and it is not considered as missing or unknown.

The tests performed are shown below in

[Table 6-1 Clinical Laboratory Safety Assessments](#)

6.2.4.1 Conversion to the International System of Units

All laboratory data will be stored in the database with the units in which they are originally reported. Laboratory data in summary tables and by-participant data listings will be presented in the International System of Units (SI units; *Système International d’Unités*). Laboratory data not reported in SI units will be converted to SI units before further processing or data analysis, unless otherwise specified.

Table 6-1 Clinical Laboratory Safety Assessments

| Test | Analytes |
|-----------------------------|---|
| Hematology | Absolute neutrophil count, hemoglobin, hematocrit, MCH, MCV, MCHC, white blood cells, red blood cells, platelet count, and differential count (neutrophils, lymphocytes, monocytes, basophils, eosinophils). |
| Chemistry (serum or plasma) | Sodium, potassium, chloride, calcium, glucose, bicarbonate, albumin, total protein, creatinine, HbA1C, blood urea nitrogen or urea, aspartate aminotransferase, alanine aminotransferase, gamma glutamyl transpeptidase, alkaline phosphatase, phosphorous, total bilirubin (direct and indirect), amylase, cholesterol (total, LDL, HDL), triglycerides, uric acid, creatine phosphokinase, lactate dehydrogenase, magnesium, C-reactive protein. Thyroid-stimulating hormone, folic acid, vitamin B12, and viral serology (HIV-1 or HIV-2 antibody and antigen, hepatitis B surface antigen, total hepatitis B core antibody, HCV antibody/RNA) will also be assessed at screening only. |
| Coagulation | Prothrombin time with INR, activated partial thromboplastin time |
| Urinalysis | Dipstick (pH, specific gravity, glucose, protein, ketones, blood). Microscopic analysis in the event of abnormal dipstick results (urinary sediment, red blood cells, white blood cells, casts, crystals, epithelial cells, bacteria). |

Abbreviations: HbA1C =hemoglobin A1C; HCV=hepatitis C virus; HDL=high density lipoprotein; HIV=human immunodeficiency virus; INR=international normalized ratio; LDL=low density lipoprotein; MCH=Mean Corpuscular Hemoglobin; MCHC=Mean Corpuscular Hemoglobin Concentration; MCV=Mean Corpuscular Volume.

6.2.5 Electrocardiogram (ECG)

Single 12-lead ECGs including heart rate, QRS (Q wave, R wave, S wave) duration, QT interval (beginning of Q wave to end of T wave) corrected using the Fridericia formula (QTcF interval), RR interval (time between 2 successive R waves) and result interpretation will be captured on the electronic CRF. The investigator will assess and document whether the ECG is “Normal”, “Abnormal not clinically significant”, “Abnormal clinically significant” or “Not evaluable”.

ECG parameters will include the following:

- Heart Rate (beats/min)
- QRS duration (msec)

- RR Interval (msec)
- QTcF Interval (msec)
- Interpretation

6.2.6 Vital Signs

Vital signs (supine systolic blood pressure, diastolic blood pressure, pulse rate, respiratory rate, and temperature) will be measured at all visits. Height will be collected at Screening of both studies. Weight will be collected at scheduled visits (refer to the protocols for scheduled visits).

Vital signs parameters will include the following:

- Weight (kg)
- Systolic Blood Pressure (millimeter of mercury (mmHg))
- Diastolic Blood Pressure (mmHg)
- Pulse Rate (beats/min)
- Respiratory Rate (breaths/min)
- Temperature (C)

6.2.7 Magnetic Resonance Imaging (MRI) for Detection of ARIA-E and ARIA-H

A brain MRI will be performed to detect brain abnormalities, such as ARIA-E and ARIA-H.

For Integrated Analysis, definitions follow the definitions in the Core Study SAP. For LTE Analysis, definitions follow below. Note that these are restricted to events at or after the first AL002 dose in the LTE Study.

6.2.7.1 ARIA-E

6.2.7.1.1 *Event Definition*

An event of ARIA-E is defined as an MRI scan where the Brain MRI Worksheet (BMW) shows the presence of vasogenic edema.

6.2.7.1.2 *Severity Definition*

ARIA-E severity is based on radiographic severity as captured on BMWs.

6.2.7.1.3 *Resolution and Time to Resolution Definition*

- ARIA-E is considered resolved for a participant if all the subsequent MRI scans showed no ARIA-E following the last MRI scan showing ARIA-E.
- Time to resolution is defined as the number of days from the exam date of the first MRI scan showing ARIA-E to the exam date of the earliest MRI showing no ARIA-E after the last one showing ARIA-E. If a participant had a resolved but recurrent ARIA-E after the previous one was resolved, both times to resolution are included.
- If there is existing ARIA-E at LTE Baseline, it is not included as a new occurrence during LTE.

6.2.7.1.4 *Time to First Occurrence and Recurrence Definition*

- Time to the first occurrence is defined as the number of days from the first dose date in the LTE Study to the exam date of the first new MRI scan showing ARIA-E.
- For a participant, if there was an MRI scan showing ARIA-E, followed by a subsequent MRI scan not showing ARIA-E, followed by a subsequent MRI scan again showing ARIA-E, this participant is considered to have a reoccurrence of ARIA-E.

6.2.7.2 **ARIA-H**

For the MRI scans collected in the Core Study, the definitions are specified in the Core Study SAP. Definitions below are for the MRI scans collected in the LTE Study.

6.2.7.2.1 *Event Definition*

For the MRI scans collected in the LTE Study, an event of new ARIA-H is defined as an MRI scan at a post-LTE Baseline visit if the overall ARIA-H radiographic severity is Mild, Moderate or Severe as captured on BMWs.

6.2.7.2.2 *Severity Definition*

For the MRI scans collected in the LTE Study, new ARIA-H overall severity and individual component severity are based on the radiographic severity as captured on BMWs.

6.2.7.2.3 *Time to First Occurrence Definition*

Definition is the same as the time to first occurrence definition for ARIA-E.

6.2.8 **Neurological Examination**

A complete neurologic examination including the evaluation of consciousness, orientation, cranial nerves, motor and sensory system, coordination and gait, and reflexes will be performed at scheduled visits (refer to the Schedules of Assessments in the protocols for scheduled visits). CFBs abnormalities should be recorded at each subsequent neurologic examination. New or worsened abnormalities should be recorded as AE on the AE electronic CRF if considered clinically significant in the Investigator's opinion.

6.2.9 **Ophthalmological Examination**

Ophthalmologic exams include the following:

- A visual acuity exam (e.g., using a Snellen chart)
- Slit-lamp examination before and after dilation
- Dilated exam of the fundus by indirect ophthalmoscopy
- Optical coherence tomography (OCT) exam, including enhanced depth imaging OCT for examination of the choroid

Ophthalmological assessments will be recorded at scheduled visits (refer to the Schedules of Assessments in the protocols for scheduled visits). CFBs abnormalities are recorded at each subsequent ophthalmological examination. New or worsened abnormalities should be recorded as AE.

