#### **7.6.4. Recording of ARIA-H and ARIA-E as Adverse Events of Special Interest**

Findings of ARIA-E or ARIA-H on MRI are determined by the MRI Central Reader (see [Section 6.3.12](#) for more detail). Once confirmed by the BMW report, ARIA-H and ARIA-E will be captured as such on the AE eCRF and marked as AESI. For definitional details of ARIA-H and ARIA-E see [Section 7.11](#). For details on how to enter AESI of ARIA in the AE eCRF, please see the CRF Completion Guidelines.

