## 7.11. Amyloid-Related Imaging Abnormalities

Among the brain abnormalities detected on MRI are ARIA, which are believed to reflect leakage of proteinaceous fluid or other blood products into the leptomeninges or brain parenchyma. The term ARIA was originally coined to describe specific brain abnormalities seen on MRI in anti-amyloid clinical trials. Although MRI findings potentially caused by AL002 may or may not be related to disruption/mobilization of, or a reaction to, amyloid species in the brain parenchyma or vasculature, the term ARIA will be used in this protocol to describe such findings until the biological mechanism is better understood. Specifically, according to the convention developed to describe ARIA occurring in clinical trials of anti-amyloid immunotherapies, ARIA-E will refer to MRI findings of vasogenic edema and leptomeningeal/sulcal effusion, and ARIA-H will refer to MRI findings of cerebral microhemorrhages, leptomeningeal hemosiderosis (also known as superficial siderosis of the CNS), and cerebral macrohemorrhages.

For the purpose of this protocol, 4 categories of ARIA will be tracked (see [Section 7.6.4](#) for recording of AESIs of ARIA). These categories are ARIA-E, ARIA-H cerebral microhemorrhages, ARIA-H leptomeningeal hemosiderosis, and ARIA-H cerebral macrohemorrhages. Symptoms associated with ARIA-H and ARIA-E will be captured as separate AEs on the AE eCRF and linked to the applicable ARIA AE line number. All clinical signs and symptoms that are identified as associated with an ARIA finding will be entered as separate AEs on the AE eCRF. Based on evaluation of the participant for signs and symptoms, and review of safety findings by the Sponsor that possibly indicates the presence of ARIA, the Sponsor may request an unscheduled MRI be obtained.

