To maintain consistency of reporting across clinical sites, findings of ARIA-E or ARIA-H on MRI are determined by the MRI Central Reader by radiologists with expertise in assessing for ARIA and other abnormalities on brain MRI. ARIA-E, ARIA-H, and other findings are documented on and reported to the sites with the BMW report (see [Section 6.3.12](#)). The BMW provided by the central reader after each MRI examination scores ARIA-E (parenchymal vasogenic edema, leptomeningeal/sulcal effusion) according to: extent, location, number of sites involved, radiographic severity (mild, mild+, moderate, moderate+, severe), and changes since prior MRI exams. ARIA-E findings typically resolve radiographically and will be noted as such on the BMW of follow-up MRI scans. The BMW also documents occurrence and characteristics (location, size, number) of ARIA-H (parenchymal microhemorrhages and leptomeningeal hemosiderosis and macrohemorrhages). Radiographic severity of ARIA-H findings (“mild”, “moderate”, “severe”) is defined as follows for the 3 categories of ARIA-H ([Table 7](#)):

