2. STUDY OBJECTIVES AND ENDPOINTS

The study objectives and endpoints are provided in [Table 2-1](#).

Table 2-1. Study Objectives, Endpoints and Estimands for LTE

| Primary Objectives | Primary Safety Endpoints and Primary Estimand |
|--|---|
| 
To evaluate the long-term safety and tolerability of AL002 in participants with AD.
 | 
Part 1: Primary Safety Endpoint and Estimand:
 
 • Treatment condition: Group T-T (AL002 15 mg/kg, 40 mg/kg or 60 mg/kg IV Q4W) continues their Core Study treatment in the LTE Study; Group P-TC treated with Placebo in the Core study will be titrated to 60 mg/kg of AL002 in the LTE study. • Target population: adult participants with AD excluding apolipoprotein E (APOE) epsilon 4 (e4)-homozygous (e4/e4) participants. • Primary endpoints: AESI incidence and SAE incidence over all weeks. • Accounting for intercurrent events: a composite strategy will be used to handle intercurrent events as below: 
 ○ Hypothetical strategy for handling premature study drug discontinuation for any reason (AEs with a start date more than 90 days after study drug discontinuation are not counted) ○ Treatment policy strategy for handling all other intercurrent events. • Population-level summaries: the descriptive statistical summaries for each treatment group of incidence rates for all AESIs and SAEs over similar periods of time. 
Part 2: Primary Safety Endpoints:
 
 • Changes from baseline (CFBs) in vital signs, physical findings, neurological findings, ophthalmological findings, ECG findings, and clinical laboratory results. • MRI abnormalities (ARIA events) • C-SSRS. 
Primary Estimand for Safety Endpoints Above:
 
The estimand for the Part 2 endpoints is defined with similar attributes as for the Part 1 estimand except applied to the different endpoints
 |

| Primary Objectives | Primary Safety Endpoints and Primary Estimand |
|--|---|

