- TEAEs by SOC and Preferred Term
- TEAE leading to study drug interruption,
- SAEs
- TEAE leading to death

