All of the MRI summaries described above will also be provided separately for participants with the following APOE genotype(s) (1) e4 carriers (including e2/e4, e3/e4 and e4/e4), and (2) non-e4 carriers (excluding e2/e4, e3/e4 and e4/e4).

For Integrated Analysis, all summaries described in this section will be provided for events across two studies as defined in Section 7.4.1.2. For LTE Analysis, only the overall summary of ARIA will be provided for events during the LTE Study.

For Integrated Analysis, the difference in proportion of participants with ARIA-E events between a slower titration rate over 48 weeks and a faster titration rate over 48 weeks will be estimated by the Cochran-Mantel-Haenszel (CMH) method adjusting for the APOE e4 status. The faster titration rate will be represented by data from the AL002 60 mg/kg treatment group during the first 48 weeks of the Core Study among participants who were on dose titration (i.e., received the first dose on or after July 22, 2021 in the Core Study) and had at least one evaluable post-baseline MRI scan. The slower titration rate will be represented by data from the first 48 weeks of the LTE Study, among Titration Cohort participants who had at least one evaluable post-baseline MRI scan in the LTE Study. Both 90% and 95% CIs for the difference in the ARIA-E events and p-value will be reported from the CMH method. The same analysis will be repeated for ARIA-H.

The statistical tests (the CMH method) of ARIA events between the slower and faster titration groups will not be performed at the first IA at the time of unblinding of the Core Study due to limited data from the LTE study at this IA, but will be performed in all analyses after the first IA.

In the Integrated Analysis, the Kaplan-Meier curves for the time to the first occurrence of ARIA-E during both the Core and LTE Studies will be plotted. For participants who experienced at least one ARIA-E, the time to the first occurrence of ARIA-E is the time from the first dose date to the onset date of the first ARIA-E occurrence. For participants who did not experience ARIA-E, the censor date will be the earlier date of the last MRI scan date, any death date, and the last dose date plus 90 days. Similarly, the Kaplan-Meier curves for the time to the first occurrence of ARIA-H will be plotted.

All MRI findings will be listed.

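### The SAP's LTE definition of an ARIA-E event requires vasogenic edema, so participants with sulcal effusion only would be left out of the LTE overall ARIA summary

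*SAP*

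**What the plan says.** SAP 6.2.7 separates two cases. The Integrated Analysis takes its ARIA definitions from the Core Study SAP; the LTE Analysis uses the definitions printed in the LTE SAP. Under 6.2.7.1.1, an LTE scan is an ARIA-E event if the BMW "shows the presence of vasogenic edema". Effusion is not mentioned there, and no other part of the SAP adds it. Severity, in 6.2.7.1.2, is the radiographic severity on the BMW.

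Protocol 7.11 uses two components: "ARIA-E will refer to MRI findings of vasogenic edema and leptomeningeal/sulcal effusion". It also says that the central reader's worksheet "scores ARIA-E (parenchymal vasogenic edema, leptomeningeal/sulcal effusion") by extent, location, number of sites and a five-level grade. On recording, protocol 7.6.4 says: "Once confirmed by the BMW report, ARIA-H and ARIA-E will be captured as such on the AE eCRF and marked as AESI".

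For ARIA-H the SAP takes a different route. Under 6.2.7.2.1 a post-baseline LTE scan is an event "if the overall ARIA-H radiographic severity is Mild, Moderate or Severe as captured on BMWs".

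On outputs, SAP 7.4.8 says: "For LTE Analysis, only the overall summary of ARIA will be provided for events during the LTE Study". SAP 7.4.3 lists "TEAEs by SOC and Preferred Term" among the LTE adverse event tables. SAP Section 1 states that the SAP prevails where it differs from the protocol.

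**The concern.** The SAP's event definition names one of the two findings that the protocol calls ARIA-E. A scan with leptomeningeal or sulcal effusion and no parenchymal edema is ARIA-E to the protocol, to the central reader and to the site completing the AE form. Under SAP 6.2.7.1.1 it is not an ARIA-E event. Because the SAP takes precedence, the protocol's wider wording cannot be used to repair the gap.

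ARIA findings on MRI are listed among the Part 2 primary safety endpoints in SAP Table 2-1, and the LTE safety summaries include a Titration Cohort column (SAP 7.4.1.1). If any participant has effusion-only ARIA-E during the LTE, the overall ARIA summary reports too low an incidence. The LTE table of adverse events by preferred term, fed by worksheet-confirmed entries on the AE form, would still count that participant. A reader would find two ARIA-E counts for the same study period and no explanation for the gap.

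**Working it through.** The main check is a comparison of definitions. The arithmetic only gives the size per affected participant.

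**1. What happens to an effusion-only LTE scan**

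| Step | Source | Result |
|---|---|---|
| Is it ARIA-E? | Protocol 7.11 | Yes: effusion is a named component |
| Does the worksheet score it? | Protocol 7.11 | Yes: both components are scored and graded |
| Is it recorded as an AESI? | Protocol 7.6.4 | Yes, once the worksheet confirms it |
| Does it have an ARIA-E severity? | SAP 6.2.7.1.2 | Yes: the worksheet grade |
| Is it an ARIA-E event in the LTE Analysis? | SAP 6.2.7.1.1 | No: edema is required |
| Does the protocol definition override that? | SAP Section 1 | No: the SAP prevails |

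The same scan therefore has an ARIA-E severity but is not an ARIA-E event. The ARIA-H rule cannot produce this conflict, because there any severity grade makes the scan an event.

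**2. Which outputs are affected**

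- LTE overall ARIA summary (SAP 7.4.8): affected. It is the only MRI-based ARIA table in the LTE Analysis.
- AESI and TEAE tables: not affected. They come from the AE form.
- Integrated ARIA summaries, Kaplan-Meier curves and the Cochran-Mantel-Haenszel comparison of slower with faster titration: these belong to the Integrated Analysis and follow the Core Study SAP. That document is not available here, so nothing can be concluded about them.

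**3. Size per affected participant**

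The SAP gives no figure to reproduce on this point. From SAP 3.5, 220 eligible Core Study participants and 80% to 90% roll-over give N = 0.80 × 220 = 176 to 0.90 × 220 = 198.

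A participant drops out of the count only if every LTE ARIA-E finding in that participant is effusion-only. Each such participant lowers incidence by 1/N.

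- AL002 total: 1/198 = 0.51 to 1/176 = 0.57 percentage points.
- One arm, assuming four equal arms (average size 176/4 = 44 to 198/4 = 49.5): 1/49.5 = 2.0 to 1/44 = 2.3 points.
- One arm, assuming sizes from 60 down to 30: 1/60 = 1.7 to 1/30 = 3.3 points.

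**4. Size as a share of incidence**

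If a share f of participants with ARIA-E have effusion only, the LTE summary reports (1 − f) of the protocol-defined incidence. The documents do not give f. Illustrative values: f = 0 gives 100%, f = 0.10 gives 90%, f = 0.30 gives 70%.

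**The case against.** The strongest counter-argument is that vasogenic edema is shorthand here. The E in ARIA-E stands for edema, and protocol 7.11.2 uses a faint area of vasogenic edema as its example of ARIA that the central reader missed. The other ARIA-E rules in SAP 6.2.7.1 refer to scans showing ARIA-E or to worksheet severity. SAP 7.4.8 summarises ARIA-E by radiographic severity, so a programmer who builds the table from the severity field would include effusion-only scans. The SAP is also meant to be read together with the protocol and the case report forms, and the worksheet layout is not available here.

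That reading is possible, but the SAP does not state it. The protocol lists edema and effusion as separate components. The counting rules in 7.4.8 refer to records indicating ARIA-E, and the only definition of an ARIA-E event for the LTE Analysis is 6.2.7.1.1. If shorthand was intended, the correction simply records the intention.

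Three further points limit the consequence, and they stand:

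- Nothing is lost from reporting altogether. All MRI findings are listed, and confirmed cases are AESIs. Neither corrects the summary table.
- The MRI summary and the adverse event table could differ for other reasons. The MRI rule, for example, does not count ARIA-E already present at LTE baseline as new. A difference between the tables would not by itself identify this problem.
- The 1/N figures hold for any single misclassified participant. They give a scale and are not evidence that anyone is misclassified.

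**Conclusion.** The point holds. As written, the LTE definition of an ARIA-E event is narrower than the protocol's and the worksheet's, and it conflicts with the SAP's own severity rule. The consequence is confined to one descriptive table, the LTE overall ARIA summary, which reports a primary safety endpoint.

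The total effect is unknown and may be zero, because the effusion-only share is not given. Per affected participant it is 0.51 to 0.57 percentage points in the AL002 total, using the SAP's expected enrolment. Within one arm it is about 2.0 to 2.3 points if the four arms are equal, which is an assumption. The conclusion also assumes that the event definition is programmed literally. It should be corrected, but it is not a threat to the trial's main comparisons on the evidence available.

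**What to change.** Replace the sentence in SAP 6.2.7.1.1 with a definition along these lines: *an ARIA-E event is an MRI scan for which the BMW reports ARIA-E, whether parenchymal vasogenic edema, leptomeningeal/sulcal effusion or both, that is, any ARIA-E radiographic grade from mild to severe.* This has the same form as the ARIA-H rule in 6.2.7.2.1. Add that references to scans showing ARIA-E elsewhere in 6.2.7.1 carry this meaning.

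Then check the ARIA-E definition in the Core Study SAP and state in the LTE SAP that the integrated titration comparison applies one rule to Core and LTE scans. If the Core Study SAP also names edema alone, changing only the LTE sentence would leave the two analyses on different definitions. In that case the definition used for the integrated ARIA analyses needs the same correction.

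The cost is one SAP sentence, one clarifying line and one document check, with a matching edit for the integrated analyses if the check shows it is needed. Both components are already scored on the worksheet, so no new data are required.
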